Thermal testing procedures. Thermal stimuli will be delivered to the (most) affected knee and/or to the ipsilateral forearm and/or thenar eminence, in randomized order, using a Medoc Pathway Thermal Sensory Analyzer (Ramat Yishai, Israel). Heat pain threshold will be assessed at each site, followed by heat pain tolerance and temporal summation. Heat pain thresholds and tolerances will be assessed using an ascending method of limits as in previous studies.^{5,12,57} Temporal summation of thermal pain will be assessed using the same stimulus parameters as previously reported by us and others.^{5,12,57} To measure Cold Pressor Pain, a modified cold-pressor procedure will be conducted. Each participant will complete a series of 60-second immersions in cold water baths at 10°C, with water temperature maintained ($\pm 0.1^\circ\text{C}$) by a refrigeration unit. Participants will immerse their left hand up to the wrist with their fingers spread apart. Participants will report when they first feel pain, and this time point will be recorded as the pain threshold. Then, they will continue for one minute or until they report intolerable pain. If a participant terminates early, the time at which they terminate will be recorded as pain tolerance. Participants will be prompted to rate the intensity of the cold-pressor pain at 30-sec intervals.

Conditioned Pain Modulation (CPM) will be used to assess pain-inhibitory function. The conditioning stimulus will be the cold pressor task applied to the left hand, which will be tailored for each participant to achieve a stimulus that produces moderate pain (i.e., a rating of 40-60 on the 0-100 scale) and can be tolerated for a 60-second period. The test stimulus will be heat pain applied to the opposite ventral forearm, at a stimulus intensity which produces moderate but tolerable pain. First, baseline heat pain responses will be assessed, after which the participant will immerse their hand in the cold water bath for 60 seconds. Immediately afterwards the heat pain will again be applied to the opposite arm and pain ratings will be obtained.

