Participants: *This study will be ancillary to one of primary mentor [name] ongoing studies, significantly increasing feasibility.* Thus, participant data for this phase will be collected from **previously obtained** experimental pain outcomes (QST), cognitive outcomes, self-reported demographic variables (age, sex/gender, race/ethnicity, education, household income), other covariate (depression, anxiety, smoking, body mass index) information due to their known influence on pain outcomes, as well as previously collected and stored blood samples (n=50). Additionally, **we plan on enrolling 40 more participants** into the PANDA study that do not meet the inclusion/exclusion criteria of the parent UCOPE study. Based on power-analytic considerations, we plan to obtain data for a total of 90 individuals of both sexes (approx. 50% male) from various ethnicities. This sample size includes a 20% attrition rate. Older adults over 55 years of age who meet American College of Rheumatology clinical criteria for knee OA⁷⁸ of at least six months duration, experience pain on more days than not, with moderate pain at baseline (i.e., > 3/6 in the VDS), and who have elevated levels of plasma IL-6 (>2.5 pg/ml) will be considered for participation. Both community-based and clinic-based recruitment methods established in our labs will be utilized. We will also utilize IRB approved registries to contact potential participants.

Exclusion criteria will align with study and safety requirements related to 1) **Pain testing:** participants will be excluded if they have concurrent medical or arthritic conditions that could confound symptomatic knee OA-related outcomes or coexisting disease that could preclude successful completion of the protocol including: systemic rheumatic condition (e.g. rheumatoid arthritis, systemic lupus erythematosus, fibromyalgia); a history of clinically significant surgery to the index knee; uncontrolled hypertension (>150/95); poorly controlled diabetes (HbA1c>7%); cardiovascular or peripheral arterial disease; serious psychiatric disorder requiring hospitalization within the past twelve months or characterized by active suicidal ideation; diminished cognitive function that would interfere with completion of study procedures (i.e., MoCA score < 25)];⁸¹ and 2) **pregnant individuals will be excluded;** and 3) **enrolled in another interventional research study.**

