Thermal testing procedures. Thermal stimuli will be delivered to the (most) affected knee and/or to the ipsilateral forearm and/or thenar eminence, in randomized order, using a Medoc Pathway Thermal Sensory Analyzer (Ramat Yishai, Israel). Heat pain threshold will be assessed at each site, followed by heat pain tolerance and temporal summation. Heat pain thresholds and tolerances will be assessed using an ascending method of limits as in previous studies.^{5,12,57} Temporal summation of thermal pain will be assessed using the same stimulus parameters as previously reported by us and others.^{5,12,57} To measure Cold Pressor Pain, a modified cold-pressor procedure will be conducted. Each participant will complete a series of 60-second immersions in cold water baths at 8°C, with water temperature maintained (+0.1°C) by a refrigeration unit. Participants will immerse their left hand up to the wrist with their fingers spread apart. Participants will report when they first feel pain, and this time point will be recorded as the pain threshold. Then, they will continue for one minute or until they report intolerable pain. If a participant terminates early, the time at which they terminate will be recorded as pain tolerance. Participants will be prompted to rate the intensity of the cold-pressor pain at 30-sec intervals.

Conditioned Pain Modulation (CPM) will be used to assess pain-inhibitory function. The conditioning stimulus will be the cold pressor task applied to the left hand, which will be tailored for each participant to achieve a stimulus that produces moderate pain (i.e., a rating of 40-60 on the 0-100 scale) and can be tolerated for a 60-second period. The test stimulus will be heat pain applied to the opposite ventral forearm, at a stimulus intensity which produces moderate but tolerable pain. First, baseline heat pain responses will be assessed, after which the participant will immerse their hand in the cold water bath for 60 seconds. Immediately afterwards the heat pain will again be applied to the opposite arm and pain ratings will be obtained.

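### PANDA pools stored UCOPE sensory data with new tests at a different written cold-pressor temperature (10°C versus 8°C) and plans no cohort or temperature term, which adds noise and may bias its cold-pressor analyses

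*Combined protocol and SAP*

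**What the plan says.** UCOPE section 6, Thermal testing procedures: "Each participant will complete a series of 60-second immersions in cold water baths at 10°C".

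PANDA section 6, Thermal testing procedures, has the same sentence but with "cold water baths at 8°C".

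The rest of the cold-pressor procedure reads the same in both: the left hand is immersed to the wrist, threshold is the time of first pain, immersion ends at one minute or at intolerable pain, ratings are taken at 30-second intervals, and the bath is regulated to 0.1°C.

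PANDA section 6, Participants, draws on data already obtained in the parent study, including "experimental pain outcomes (QST), cognitive outcomes, self-reported demographic variables", with stored blood samples from 50 people. It then adds: "we plan on enrolling 40 more participants", who are people "that do not meet the inclusion/exclusion criteria of the parent UCOPE study". The combined target is 90.

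PANDA section 6, Hypotheses and data-analytic strategy, uses experimental pain outcomes in the H1a regressions on DII. The covariates named are BMI and smoking (as examples), then age, race and sex. Neither cohort nor bath temperature appears, and the difference between the two sections is not mentioned.

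**The concern.** In a cold-pressor test the bath temperature is the stimulus. Followed as written, the plan merges responses to two stimuli and analyses them as one variable. Cold-pressor threshold, tolerance and ratings would then carry a shift that depends only on which study tested the person.

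The shift does two things. It adds variance to the outcome in every model that uses it. It also becomes a confounder wherever cohort is associated with the exposure, which is DII in H1a, or pain-impact group if these outcomes are compared across groups. The 40 new participants are selected for being ineligible for UCOPE, so there is no reason to expect cohort to be independent of either. Nothing in the plan would detect or remove the effect.

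**Working it through.** **Inputs from the documents.** Bath temperature 10°C (UCOPE) and 8°C (PANDA); 50 stored and 40 new participants; three pain groups; threshold 0.05, two-tailed.

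**The plan's own figure.** 50 + 40 = 90, which reproduces the stated total. On these figures 40/90 = 44% would be tested at 8°C and 50/90 = 56% at 10°C. PANDA gives no effect size, SD or power, so no power figure can be checked.

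**Assumptions, not in the documents.** Stored data at 10°C and new data at 8°C. The temperature shift in a cold-pressor outcome is d = 0.2, 0.5 or 0.8 within-cohort SD. Group sizes and the split of cohorts across groups are not stated, so three groups of 30 and four splits are tried.

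**Noise.** With share p = 40/90 at one temperature, p(1 − p) = 0.247. Outcome variance is multiplied by 1 + 0.247d², which is 1.01, 1.06 and 1.16 for the three shifts. As noise alone this is modest.

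**Bias in the H1a regression on DII.** Let mean DII differ between cohorts by Δ within-cohort SD (also unknown). With no true association, the spurious standardised slope is

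0.247·d·Δ / (1 + 0.247·Δ²).

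- Δ = 0: slope 0 for any d.
- d = Δ = 0.2: 0.010.
- d = Δ = 0.5: 0.0617/1.0617 = 0.058.
- d = Δ = 0.8: 0.158/1.158 = 0.136.

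The standard error of such a slope with 90 people is roughly 1/√90 = 0.105. The bias therefore runs from nothing to somewhat more than one standard error.

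**Bias in a pain-group comparison.** The spurious difference between two groups is d × (share tested at 8°C in one − share in the other). For a three-group ANOVA the noncentrality is d² × Σ 30(p_g − p̄)², where p_g is the share of group g tested at 8°C and p̄ is the mean share. Type I error then follows from the noncentral F distribution on 2 and 87 degrees of freedom.

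| New participants per group of 30 | Largest spurious difference, SD (d = 0.2 / 0.5 / 0.8) | Type I error without a cohort term (d = 0.2 / 0.5 / 0.8) |
|---|---|---|
| 14/13/13 | 0.007 / 0.017 / 0.027 | 0.050 / 0.050 / 0.051 |
| 18/13/9 | 0.06 / 0.15 / 0.24 | 0.054 / 0.075 / 0.118 |
| 25/10/5 | 0.133 / 0.333 / 0.533 | 0.072 / 0.201 / 0.457 |
| 30/10/0 | 0.20 / 0.50 / 0.80 | 0.098 / 0.393 / 0.799 |

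These error rates take the residual SD as 1 and so are slightly high, because the unmodelled shift also inflates the residual. Allowing for that, at d = 0.8 the rates become 0.03, 0.08, 0.40 and 0.78 from top to bottom. The pattern does not change. With a cohort term, type I error is 0.05 in every scenario.

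**Reach.** Only cold-pressor threshold, tolerance and ratings are directly affected. Pressure, punctate and heat procedures read the same in both sections. Conditioned pain modulation is less exposed, because its conditioning stimulus is tailored to a rating of 40 to 60. DII, epigenetic age and cognition are untouched, as is UCOPE's randomised comparison.

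**The case against.** A reader might infer that cohort differences will show up as pain-group differences. The documents do not support that, for three reasons.

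- The split of the 50 and the 40 across pain groups is not given. PANDA repeats the parent entry rules for knee osteoarthritis duration, pain frequency, pain level and IL-6. What it leaves out includes the exclusions tied to oxytocin use and to MRI, so a person can fail UCOPE for reasons unrelated to pain impact. UCOPE also recruits controls, so the stored 50 may include pain-free people. A link between cohort and pain group is possible, but neither its existence nor its direction is shown.
- A group comparison of sensory outcomes is not explicitly planned. The ANOVAs cover the variables of interest, and the only list attached to that term is DII, epigenetic age and cognitive status. The stated use of experimental pain is the H1a regression on DII, and bias there needs DII to differ by cohort.
- The 10°C for the stored records is inferred from the current UCOPE text. PANDA carries over other parent wording that does not fit an observational study, such as a reference to a post-intervention assessment, so a copying or version discrepancy with one temperature used in practice is also consistent with the documents.

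It is also tempting to argue from the 2°C gap being twenty times the 0.1°C regulation limit. That limit says how steadily the bath is held, not how far 2°C moves a pain outcome.

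All of this stands, and it makes the bias conditional. It does not remove the contradiction between the sections, the pooling, or the absence of any adjustment. If 8°C is a slip, the line still needs correcting, because it is the written instruction for testing new participants.

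**Conclusion.** The concern holds in a conditional form. As written, PANDA pools cold-pressor data from two bath temperatures and has no means of accounting for it. If the stored records were taken at 10°C, the certain consequence is extra variance, about 1% to 16% for shifts of 0.2 to 0.8 SD. Bias in the DII regressions arises only if DII differs by cohort. Bias in a pain-group comparison arises only if cohort and pain group are associated.

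The size cannot be fixed from the documents: it is about zero with balanced cohorts and substantial with strong separation. The shifts, group sizes and splits behind these figures are assumptions. The issue is confined to the cold-pressor outcomes of an observational ancillary study, but it is avoidable at almost no cost.

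**What to change.** 1. Establish and document the bath temperature used for each stored and new record.
2. Reconcile the UCOPE and PANDA thermal testing sections so that new participants are tested at the same temperature as the stored records. Which temperature that is, is for the investigators to settle.
3. If temperatures did differ, report the cohort-by-pain-group table and mean DII by cohort, and include a cohort/temperature term in every model that uses a cold-pressor outcome.
4. Where cohort and pain group largely coincide, analyse within cohort instead. If they coincided completely, no covariate could separate them. Tolerance needs particular care: it is capped at one minute, so temperature may change how many people reach the cap, and a simple mean-shift term handles that poorly.

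The cost is one line of the PANDA procedure if testing can still be aligned. Otherwise it is one recorded field, one table and one covariate. Aligning before further testing is the safer course, because it does not depend on how the cohorts overlap.

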
Rigor of the prior research. There are noted gaps and weaknesses of the prior research that need to be addressed in order to move this field forward that this application plans to address. Historically, the consideration of pain impact has been overlooked, likely leading to inconsistent results among the literature observing the

relationship between AD/ADRD and chronic pain. Additionally, studies implicating lifestyle factors such as nutrition as a possible mechanism influencing the relationship between pain and cognitive disease have not been completed, despite evidence of nutrition status influencing on both disease states independently. Finally, the examination of epigenetics (influenced by nutrition) such as DNA methylation and epigenetic/cellular aging as a common mechanism driving both pain and AD/ADRD in tandem has not been appreciated. This proposal not only will provide the candidate with the opportunity to train in an outstanding research environment, but also allow her to contribute to filling the gaps in the literature that will allow the field to progress towards solutions to solve the complex problems seen in chronic pain and AD/ADRD.

5. Specific Aims

Specific Aim 1: Determine the association among DII, epigenetic clocks/cellular aging and cognitive function middle-age and older adults with low-impact pain, high-impact pain and pain free controls.

Hypotheses 1a-d: Individuals with chronic pain will (H1a) have a more positive/inflammatory DII, which will be associated with (H1b) accelerated epigenetic aging and (H1c) greater cognitive impairment. These associations will be more significant in the high-impact pain group compared to those with (H1d) low-impact pain and pain-free controls.

6. Research Plan

We propose a cross-sectional, observational study design that will assess the relationship between pain, cognition and dietary pattern in older adults with and without symptomatic knee OA pain. This will be completed in 2 experimental sessions approximately one week apart. After initial screening, eligible participants will undergo the sessions (health and sensory sessions) for collection of clinical, functional (physical, cognitive, emotional), QST, and blood-based biomarker data lasting 2-3 hours.

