Hypotheses and data-analytic strategy: Prior to the testing of proposed hypotheses, each variable will be carefully examined to identify missing values, statistical outliers, and violations of relevant assumptions (i.e., Durbin-Watson, Shapiro-Wilk). Sensitivity analyses would then be completed to examine differences in results between variables with missing data and those same variables with data imputation. A corrected threshold will be set to 0.05, two-tailed. Descriptive statistics will be computed and represented as percentages or means (standard deviations). Group differences (pain impact groups; Vitamin A and D clinical cutoff differences) among potential covariates of interest will be examined using a series of one-way analysis of variance tests (ANOVAs) with follow-up/post hoc Bonferroni corrections. All participants will be matched on race and sex due to their relationships with pain and cognitive outcomes. All statistical analyses employed in this study were performed using SPSS (IBM) version 28.0 (IBM; Armonk, NY). Specific to hypotheses 1a-d: Sequential hierarchical multiple regression models will be employed to investigate the extent to which the continuous DII variable is associated with (H1a) greater severity, duration, and frequency of experimental and clinical pain outcomes, (H1b) accelerated epigenetic aging, and (H1c) worse cognitive decline between individuals with and without pain. Analyses of Variance (ANOVAs) will be performed in order to examine differences in variables of interest between groups: high-impact chronic pain, low-impact pain, and pain free controls. Additionally, three separate sequential hierarchical regression models within each group will be used to examine the extent to which higher scores DII scores are associated with epigenetic aging and cognitive outcomes. Variables of interest (DII, epigenetic age, cognitive status) will be entered into *step 1* of the analysis, relevant clinical covariates (e.g., BMI, smoking) will be entered in *step 2* of the hierarchical regression models, and relevant demographic variables (i.e., age, race, sex, etc.) in *step 3* of the regression models. Finally, a modified Poisson-regression analysis will be performed to assess the relative risk of clinical cognitive impairment between pain impact groups.

7. Possible Discomforts and Risks

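### PANDA hypothesis H1d claims a stronger diet association in high-impact pain, but no planned analysis compares the association between the pain-impact groups

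*Combined protocol and SAP*

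**What the plan says.** PANDA section 5 (Specific Aims) ends its list of hypotheses with a comparison between groups: "These associations will be more significant in the high-impact pain group compared to those with (H1d) low-impact pain and pain-free controls". The associations meant are those of DII with epigenetic aging and with cognitive impairment.

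PANDA section 6, under the hypotheses and data-analytic strategy, assigns four kinds of analysis to hypotheses 1a to 1d:

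- Regressions of the outcomes on DII for H1a to H1c, the last of them described as "worse cognitive decline between individuals with and without pain".
- Analyses of variance, which "will be performed in order to examine differences in variables of interest between groups: high-impact chronic pain, low-impact pain, and pain free controls".
- Fits by group: "three separate sequential hierarchical regression models within each group will be used". Their outcomes are the epigenetic and cognitive measures, with the DII score as predictor.
- Finally, "a modified Poisson-regression analysis will be performed to assess the relative risk of clinical cognitive impairment between pain impact groups".

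The order of entry in the regressions is given: "Variables of interest (DII, epigenetic age, cognitive status) will be entered into *step 1* of the analysis", followed by clinical covariates and then demographic variables. No step contains a pain-impact group term or a DII-by-group product. The significance threshold is 0.05, two-tailed.

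The Participants paragraph gives a total of 90 (50 with existing data and 40 to be enrolled), with 20% attrition included. It gives no group sizes, effect size or power.

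**The concern.** H1d is a statement about a difference in slopes: the DII slope in high-impact pain against the slope in each of the other two groups. A slope that is significant in one group and not in another is weak evidence that the two slopes differ. With groups this small, each within-group test has moderate power at best, so equal true slopes will often give unequal verdicts. A group with more participants will also tend to have the smaller p-value whatever its slope.

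At stake is whether a published statement that the association is stronger in high-impact pain has a known error rate. PANDA's background section argues that chronic pain must be stratified by impact, and H1d is the hypothesis that uses that stratification for the DII associations.

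**Working it through.** **1. Does any planned analysis compare slopes between impact groups?**

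| Planned analysis | What it compares | Tests a slope difference between impact groups? |
|---|---|---|
| Regressions for H1a to H1c | DII association, pain vs no pain | No: two categories, no interaction listed, high and low impact not separated |
| Analyses of variance | Means across the three groups | No |
| Within-group regressions | DII association, one group at a time | No: estimated separately, never contrasted |
| Modified Poisson regression | Risk of cognitive impairment by group | No: DII slope not compared |

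The phrase about three separate models within each group can mean one model per group or three per group. Neither reading contrasts slopes.

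**2. The plan's own figures.** 50 + 40 = 90, and 90 × 0.8 = 72 after attrition, so those figures agree. The power basis of 90 cannot be reproduced, because no effect size, standard deviation, power or group sizes are given. If the groups were equal (an assumption), they would hold 90/3 = 30 at enrolment or 72/3 = 24 after attrition.

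**3. How often would equal associations look different?** Assume the same true correlation r in all three groups, no covariates, and two-sided 0.05. Let p be the power of one within-group slope test (noncentral t). Then:

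- high-impact alone significant: p(1 − p)²
- high-impact significant and at least one other group not: p(1 − p²)

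| n per group | r | p | High alone | High, and at least one other not |
|---|---|---|---|---|
| 30 | 0.2 | 0.191 | 0.191 × 0.809² = 12.5% | 18.4% |
| 30 | 0.3 | 0.384 | 0.384 × 0.616² = 14.6% | 0.384 × (1 − 0.147) = 32.7% |
| 30 | 0.4 | 0.636 | 0.636 × 0.364² = 8.4% | 37.9% |
| 24 | 0.2 | 0.160 | 11.3% | 15.6% |
| 24 | 0.3 | 0.314 | 14.8% | 28.3% |
| 24 | 0.4 | 0.534 | 11.6% | 38.2% |

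Simulation with 20,000 data sets per scenario agrees: about 9% to 15% for the first pattern and about 15% to 38% for the second. A slope contrast rejects in about 5% throughout.

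Three further cases show the limits:

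- At r = 0 the two patterns occur in 0.05 × 0.95² = 4.5% and 0.05 × (1 − 0.0025) = 5.0%.
- With equal power in all groups, p(1 − p)² cannot exceed 4/27 = 14.8%.
- With an assumed split of 45/25/20 in favour of high-impact pain and r = 0.3, the three powers are 0.541, 0.326 and 0.265. High-impact alone is then significant in 0.541 × 0.674 × 0.735 = 26.8%.

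**4. What would a proper test deliver?** For high vs low with true r = 0.5 vs 0.2, use Fisher's z. The difference is 0.549 − 0.203 = 0.347, with standard error √(2/(n − 3)).

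- n = 30: 0.347/0.272 = 1.27, and Φ(1.27 − 1.96) is about 25%.
- n = 24: 0.347/0.309 = 1.12, and Φ(1.12 − 1.96) is about 20%.

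A simulated slope difference in the pooled model gives about 17% at n = 24, hence the range of 17% to 25%. For 80% power, 2 × ((1.96 + 0.84)/0.347)² + 3 gives about 134 per group.

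**5. One contrast or two?** A single contrast of high-impact against the average of the other two does not match H1d. Take r = 0.5 in both pain groups and 0 in controls. H1d is then false against low-impact pain, yet that contrast rejects in 17% (n = 24) to 21% (n = 30) of simulated studies.

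**The case against.** The strongest objection is that the plan never says H1d will be decided by comparing p-values. The within-group models are described only as examining how far DII is associated with the outcomes, and that is a legitimate descriptive use. This stands. A reader might infer a p-value rule from the wording of H1d, and the inference is natural, but the documents state no rule. The supportable defect is that no comparison of slopes is specified and the wording invites the wrong one.

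A reader might also take the pattern reaching 38% as the false-support rate. H1d is claimed against both other groups, so the matching pattern is high-impact alone significant, at about 9% to 15% for equal groups. With no association at all the rate is about 5%, and at r = 0.5 it falls to about 2% to 5%. The excess arises when a moderate common association exists.

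Two other stronger statements are not supported. The loss of pooled residual degrees of freedom is minor: with 30 per group and before covariates, the critical t is 2.05 on 28 degrees of freedom against 1.99 on 84. The documents also do not call H1d the main comparative hypothesis; H1a compares groups as well.

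Low power of the interaction test is a fair warning about the remedy. It does not rescue the separate fits: an inconclusive slope comparison is a more accurate report than a contrast of p-values.

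**Conclusion.** The point holds as a gap in the analysis plan. H1d asserts a difference in association, none of the analyses assigned to it tests one, and the remaining route is an informal reading of separate p-values.

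Under equal groups of 24 to 30, a common true correlation of 0.2 to 0.4 and no covariates, that reading would wrongly favour high-impact pain over both other groups in about 9% to 15% of studies, against about 5% for a slope contrast. Group sizes and correlations are assumptions. An unequal split that favours the high-impact group would raise the figure.

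The consequence is confined to one hypothesis of a cross-sectional, observational ancillary study. A reader might infer that the UCOPE trial is weakened too. It is not: its randomised comparison does not depend on this analysis. The change should be made, but it is not critical to the trial.

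**What to change.** - Reword H1d as a larger DII slope in high-impact pain, not as a statement about significance.
- For each outcome, fit one model over all participants with DII, pain-impact group, DII × group and the covariates already planned.
- Base H1d on two pairwise slope differences, high vs low and high vs control. Require both, and report each with a confidence interval.
- Keep the within-group fits as descriptive estimates with confidence intervals.
- Label H1d exploratory, or state its power and the expected group sizes.

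The cost is wording and one interaction per outcome (two product columns for three groups), with no new data. The downside should be disclosed. Power for high vs low alone is about 17% to 25% in the scenario above, and requiring both contrasts cannot raise it, so an inconclusive result is likely at a total of 90.

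### PANDA regressions: DII is entered before every confounder, alongside two of the study's own outcomes, and no step is named as the basis for H1a to H1c

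*Combined protocol and SAP*

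**What the plan says.** The text is in the PANDA protocol, section 6, under Hypotheses and data-analytic strategy. The method is introduced so: "Sequential hierarchical multiple regression models will be employed to investigate the extent to which the continuous DII variable is associated with" pain outcomes (H1a), epigenetic aging (H1b) and cognition (H1c). Three further regressions are planned within the pain-impact groups. The order of entry follows:

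- Step 1: "Variables of interest (DII, epigenetic age, cognitive status) will be entered into" this step.
- Step 2: "relevant clinical covariates (e.g., BMI, smoking) will be entered in" this step.
- Step 3: "relevant demographic variables (i.e., age, race, sex, etc.) in" this step.

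On significance the section says "A corrected threshold will be set to 0.05, two-tailed". It names no test statistic for the regressions and does not say which step answers each hypothesis. Participants are to be matched on race and sex only. The Participants paragraph gives the size: "we plan to obtain data for a total of 90 individuals of both sexes", and adds "This sample size includes a 20% attrition rate".

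**The concern.** Sequential entry is normally used to ask what an exposure adds once confounders are accounted for, so the confounders go in first. Here the order is the reverse. The step that contains DII is adjusted for none of BMI, smoking, age, race and sex, and steps 2 and 3 show what those covariates add. An analyst who reported the step 1 result as the DII finding would be following the plan, yet could be reporting confounding by age, BMI or smoking as a diet association.

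The predictor list raises a separate problem. Epigenetic age is the outcome of H1b and cognitive status is the outcome of H1c, but both sit beside DII as predictors. The plan does not say which is removed from which model. Taken literally, an outcome would predict itself. If only the modelled outcome is dropped, the cognition model still conditions DII on epigenetic age, the epigenetic model conditions DII on cognition, and the pain models condition DII on both. H1b and H1c ask a simpler question than any of these models answers.

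**Working it through.** **Inputs.** From the documents: the order of entry, two-sided 0.05, n = 90, and 20% attrition, so 90 × (1 − 0.20) = 72. Assumed: the three pain-impact groups are equal in size, giving 90/3 = 30 each, or 72/3 = 24 after attrition. Also assumed, because the documents give no correlations: one confounder with correlation a with DII and c with the outcome, each from 0.1 to 0.5, and no direct DII effect. The plan gives no power or R-squared figure for these models, so there is none to reproduce.

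**1. DII alone at step 1.** With no direct effect, the crude correlation of DII with the outcome is a × c. By the Fisher approximation, z = atanh(a × c) × √(n − 3), and the rejection rate is Φ(z − 1.96) + Φ(−z − 1.96).

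- n = 90, (0.5, 0.5): a × c = 0.25, z = 0.2554 × 9.327 = 2.38, rate 66%.
- n = 90, (0.35, 0.40): a × c = 0.14, z = 0.1409 × 9.327 = 1.31, rate 26%.
- n = 90, (0.2, 0.2): a × c = 0.04, z = 0.37, rate 6.6%.
- n = 72, (0.5, 0.5): z = 0.2554 × 8.307 = 2.12, rate 56%.
- n = 30, (0.5, 0.5): z = 0.2554 × 5.196 = 1.33, rate 26%.

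Simulated step 1 rejection rates (5,000 data sets per cell, equal correlations) agree:

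| n | r = 0 | 0.2 | 0.3 | 0.4 | 0.5 |
|---|---|---|---|---|---|
| 90 | 4.8% | 6.5% | 13.1% | 33.7% | 66.8% |
| 72 | 4.6% | 6.2% | 11.5% | 27.0% | 56.9% |
| 30 | 4.9% | 5.6% | 7.3% | 13.4% | 26.1% |
| 24 | 5.2% | 5.7% | 7.7% | 11.7% | 21.8% |

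At (0.1, 0.1) the rate is about 5% at every n.

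**2. DII in the fully adjusted model.** In the same simulations the DII coefficient, with the confounder and four null covariates in the model, rejects in 4.7% to 5.5% of data sets in every cell. This coefficient depends on which variables are in the model, not on the order of entry. Its t-test is the same test as the R-squared change with DII entered last; in a worked example both gave p = 0.9027.

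**3. The block as written.** Step 1 holds three variables, so its joint test is not a test of DII. Suppose DII is unrelated to everything and epigenetic age correlates 0.3 with cognition (assumed). The two-variable step 1 block for cognition is then significant in 74% of data sets at n = 90 (37% to 96% for correlations of 0.2 to 0.4).

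**4. Conditioning on another outcome.** Suppose DII acts on cognition entirely through epigenetic age, with standardised paths of 0.4 and 0.5 (assumed). The DII–cognition correlation is 0.4 × 0.5 = 0.20. At n = 90, z = 0.2027 × 9.327 = 1.89, so the DII test rejects in about 47% of studies. With epigenetic age in the model the DII coefficient has expectation zero and rejects in about 5%. Here 47% is power for a real association, which the extra predictor removes. Reversing the order of entry does not restore it.

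**The case against.** A reader might infer that the plan tests DII by its R-squared step, so that the PANDA results will be unadjusted. The documents do not support that. The section mentions neither R-squared nor a step 1 test, and the phrase about extent refers to the regression models as a whole. The planned final model already adjusts DII for BMI, smoking, age, race and sex. Exposure first, then clinical covariates, then demographics can also serve as a display that moves from crude to adjusted. This objection stands as far as it goes: on step order, the defect is an unstated basis for inference that permits an unadjusted reading, not a commitment to one.

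The size also needs restraint. All correlations are assumed, and with weak confounding almost nothing happens. The order-of-entry sentence follows directly on the within-group models, where small samples reduce the inflation. For H1b the plan uses an epigenetic measure that it calls age-adjusted, a partial answer to confounding by age. It is a simple difference, however, and does nothing for pain, cognition, BMI or smoking. Matching on race and sex does not reach those either.

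BMI may be more than a confounder. The PANDA Background cites a study in which inflammatory markers fell on a diet before weight did, so weight may lie downstream of diet. Adjusting for it could remove part of a real association. This stands and is reflected in the fix.

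The step 1 list could also be shorthand for whichever variable is of interest in a given model. That may be the intention, but the text does not say so.

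**Conclusion.** The point holds in two parts.

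First, the step containing DII is unadjusted, and the plan does not say that inference rests elsewhere. With no independent DII effect and assumed correlations of 0.1 to 0.5, a test of DII alone at step 1 rejects in about 5% to 67% of studies at n = 90, 5% to 56% at n = 72, and 5% to 26% in groups of 24 to 30 (equal split assumed). The fully adjusted coefficient stays at about 5%. The inflation is negligible at correlations of 0.2 or below and large from about 0.4. It matters only if conclusions are drawn from step 1.

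Second, and independently of order, epigenetic age and cognitive status do not belong among the predictors at any step. This is the firmer error, because even the final-step DII coefficient then fails to estimate the association that H1c (or H1b) names. The fall from about 47% to 5% illustrates one extreme, complete mediation, under assumed paths.

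Neither part reaches the randomised oxytocin comparison. PANDA is a cross-sectional observational study, and only its DII hypotheses are affected.

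**What to change.** Rewrite the order-of-entry sentence for the H1a to H1c models, overall and within groups:

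1. Enter demographics in step 1, clinical covariates in step 2 and DII alone in step 3.
2. Remove epigenetic age and cognitive status from the predictors. If the path from diet through epigenetic aging to cognition is of interest, describe it as a separate mediation analysis.
3. State that H1a to H1c rest on the DII coefficient and its confidence interval in the fully adjusted model.
4. Report the model without BMI as a sensitivity analysis.

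Item 3 alone would settle the question of step order. Item 2 is needed whatever order is kept. The cost is a few sentences; data, sample size and software are unchanged.
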